# 3.5 Pharmacodynamic Exploratory Endpoint(s) and Analyses

#### 3.5.1.1 Pharmacodynamic Endpoint(s)

- Change from baseline (Day -1) to Day 28 in GLP-1, glucagon, insulin, and c-peptide AUC0-4h as measured by MMTT
- Change from baseline (Day -1) to Days 7, 14, and 28 in fasting FFA level
- β-hydroxybutyrate profile to include AUC0-inf, AUC0-last, Cmax, and tmax
- Total glucose excreted in urine collected for 24 hours on Days 1 and 28

### 3.5.1.2 Analysis of Pharmacodynamic Endpoint(s)

PD analysis will be based on the ITT population. The change from baseline endpoints for GLP-1, glucagon, insulin, and c-peptide AUC0-4h and for fasting FFA levels will be summarized by treatment group at each time point and the final treatment evaluation time analyzed similar to the analysis of primary efficacy endpoint with LOCF approach to handle missing data.

Descriptive statistics will be provided for  $\beta$ -hydroxybutyrate parameters: AUC0-inf, AUC0-last, Cmax, and tmax at each time point and total glucose urinary excretion (Days 1 and 28). The  $\beta$ -hydroxybutyrate parameters will be calculated by the Pharmacokinetics group following the calculations provided below in the Pharmacokinetics Section.

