3.2.3.3 Exploratory endpoints

Further characterization of the additive effects of MEDI0382 in combination with dapagliflozin and metformin as dual therapy versus the dual therapy and placebo will be assessed by measuring plasma glucagon, insulin, and c-peptide after a MMTT.

It is hypothesized that the glucagon component of MEDI0382 may lead to increased fatty acid oxidation in the liver, thus resulting in increased ketogenesis. This effect alongside the dapagliflozin-induced glycosuria may predispose subjects to increase ketogenesis. Changes in serum ketones (β -hydroxybutyrate) and FFA profile are used as exploratory endpoints to investigate whether or not concomitant treatment of MEDI0382 and SGLT2 inhibitors increases the propensity to develop ketosis.

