- ^j Subjects to dose at home on Day 22 and 27 prior to coming to the clinic. Investigational product will be administered in the clinic on Days 1, 2, 7, 8, 14, 15, and 28. Please refer to Investigational Medicinal Product Manual for more details.
- ^k After investigational product administration (MEDI0382 or placebo) on Day 1 (first dose) and on Days 8 and 15 (uptitration days), subjects will be monitored for safety, glucose, and ketones. Capillary blood ketones and glucose monitoring will be done with a glucometer before meal, predose, 2 hours postdose, and 4 hours postdose. The subject will be discharge 6 hours postdose.
- ^l Outside of fasting times meals/snacks and fluid intake should be standardized across each inpatient stay.
- ^m Predose labs not applicable on Day 7, 14, 22, and 28. N-B Serum chemistry will include bicarbonate measurements.
- ⁿ **PK sampling schedule:** Blood samples for PK (MEDI0382 and dapagliflozin) to be drawn as follow:
- Dapagliflozin:
 - Day -1, 7, 14, 28: Predose; 0.5, 1, and 2 hours (\pm 15 minutes) postdose; and 4, 6, 8, and 12 hours (\pm 30 minutes) postdose
 - Day 1, 8, and 15: Predose
 - Day 29: 24 hours after dosing time on Day 28

- MEDI0382
 - Day 7, 14, and 28: Predose; 0.5, 1, and 2 hours (\pm 15 minutes) postdose; and 4, 6, 8, and 12, (\pm 30 minutes) postdose
 - Day 8 and 15: Predose
 - Day 29: 24 hours after dosing time on Day 28
- **Ketone blood sampling schedule:**
 - Blood samples for ketone (β -hydroxybutyrate) PK to be drawn following an overnight fast of at least 10 hours at the following times:
 - Day -1, 7, 14, and 28: Predose; 0.5, 1, and 2 hours (\pm 15 minutes) postdose; and 4, 6, 8, and 12, (\pm 30 minutes) postdose. A standardized breakfast meal will be provided 2-hour post dose on Day 7 and 14 (see footnote “r”)
 - Additional blood samples for ketone PK to be drawn as follow:
 - Day 1, 8, and 15: Predose
 - Day 29: 24 hours after dosing time on Day 28 (\pm 30 minutes)
- [REDACTED]

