## 2.1.3 Exploratory Study Objectives

• To compare additional measures of glucose control (fasting plasma glucose [FPG] and hemoglobin A1c [HbA1c]) in subjects treated with dapagliflozin and metformin receiving MEDI0382 or placebo for 28 days

[figure not shown]
- To evaluate pancreatic and incretin hormone AUC profiles (ie, active glucagon-like peptide-1 [GLP-1], glucagon, insulin, and c-peptide) as measured by MMTT in subjects treated with dapagliflozin and metformin receiving MEDI0382 or placebo for 28 days
- To compare the fasting free fatty acid (FFA) levels in subjects treated with dapagliflozin and metformin receiving MEDI0382 or placebo for 28 days
- To compare plasma ketone profile (β-hydroxybutyrate) in subjects treated with dapagliflozin and metformin receiving MEDI0382 or placebo for 28 days
- To compare the change in body weight after 28 days of treatment with MEDI0382 or placebo in subjects treated with dapagliflozin and metformin
- To evaluate 24-hour urinary glucose excretion in subjects treated with dapagliflozin and metformin receiving MEDI0382 or placebo

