#### 3.8 Pharmacokinetics

For MEDI0382, Dapagliflozin and β-hydroxybutyrate, actual time of sampling, rather than nominal (planned) sampling time, will be used to derive PK parameters. Nominal sampling time will be used for the summary of PK concentrations and will be utilized in the descriptive summaries in mean plots. Missing PK parameters will not be imputed.

For subjects in each treatment group the following pharmacokinetic parameters will be determined from the plasma concentration-time data for MEDI0382, dapagliflozin and  $\beta$ -hydroxybutyrate if data allow. The pharmacokinetic parameters will be calculated by standard non-compartmental analysis according to current working practices and using Phoenix WinNonlin 6.3 or equivalent:

1. Cmax: The first occurrence of the maximum observed plasma concentration determined directly from the raw concentration-time data

- 2. tmax: The first time at which Cmax is observed will be determined directly from the raw concentration-time data.
- 3. Cτ: trough concentrations from the plasma concentration-time data at the end of the dosing interval (i.e. 24 hours).
- 4. AUCτ: Area under the plasma concentration time curve at the end of the dosage interval τ.
- 5. Ro: observed accumulation ratio will be calculated using both the AUC and Ctrough methods, where data allows, as follows: Ro = AUCτdayi/AUCτday1 and Ro = Cτdayi/Cτday1.

If data allows additional parameters may be derived for MEDI0382 and Dapagliflozin such as t half: the apparent terminal elimination half-life ( $t_{1/2}$ ) obtained as the ratio of  $ln2/\lambda_z$ , where  $\lambda_z$  is the terminal phase rate constant estimated by linear regression analysis of the log transformed concentration-time data; and Cl/F: the apparent clearance calculated as  $CL/F=Dose/AUC(0-\infty)$ .

All the derived parameters described above will be listed. For each of these parameters, except for tmax, the following summary statistics will be calculated for each active treatment group: median, maximum, minimum, arithmetic mean, standard deviation, CV, geometric mean. For tmax, the following summary statistics will be calculated for each active treatment group: median, maximum, minimum, arithmetic mean.

Individual Ctrough will be listed by treatment and day and will be summarized as maximum, minimum, arithmetic mean and geometric mean.

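### The ketone objective is to compare arms, but the SAP prespecifies no between-arm ketone estimate, does not use Day -1 as a baseline, and lists an AUC0-inf unsuited to an endogenous analyte

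*SAP*

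**What the plan says.** SAP 2.1.3 words the objective as "To compare plasma ketone profile" between subjects receiving MEDI0382 and those receiving placebo; the protocol synopsis and Table 2.3-1 agree. Protocol 3.2.3.3 gives the reason: serum ketones and FFA are "used as exploratory endpoints to investigate whether or not concomitant treatment of MEDI0382 and SGLT2 inhibitors increases the propensity to develop ketosis".

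SAP 3.5.1.1 defines the endpoint as a β-hydroxybutyrate "profile to include AUC"0-inf, AUC0-last, Cmax and tmax. It is not defined as a change from baseline. SAP 3.5.1.2 then states "Descriptive statistics will be provided for" these parameters at each time point, and sends the reader to SAP 3.8 for the calculations.

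The preceding paragraph of SAP 3.5.1.2 treats the MMTT hormone AUCs and fasting FFA differently. Their changes from baseline are summarized by treatment group, "and the final treatment evaluation time analyzed similar to the analysis of primary efficacy endpoint with LOCF approach to handle missing data". The primary analysis (SAP 3.4.1.3) is an ANCOVA on baseline value and treatment.

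The footnotes to Protocol Table 4.2.3-1 schedule ketone profiles from predose to 12 hours on Days -1, 7, 14 and 28. They add predose samples on Days 1, 8 and 15, and a sample on Day 29, 24 hours after the Day 28 dose. The MMTT drink is given 2 hours after dosing on Days -1 and 28. On the other two profile days the meal is different: "A standardized breakfast meal will be provided 2-hour post dose on Day 7 and 14".

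**The concern.** The stated aim is a comparison between randomized arms, but the planned output is a set of summary tables. A reader of the study report would have no prespecified effect size for ketones, no interval around it, and no adjustment for each subject's ketone level on dapagliflozin before the first dose of injected study drug.

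This matters because Protocol 1.6.4 names increased ketosis as a theoretical risk of this particular combination, and Protocol 1.5 says the safety of MEDI0382 with an SGLT2 inhibitor should be studied before such subjects enter Phase 3. If the contrast is built after the data are seen, the choice of day, parameter, scale and baseline is open. One of the listed parameters, AUC0-inf, could also give figures that depend mostly on extrapolation.

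**Working it through.** **The plan's own figure.** The documents give no SD, effect size or power for ketones. The only quantified claim is power above 95% for the primary endpoints with 23 per arm (SAP 2.4): 30% with SD 20%, and 225 hr•mg/dL with SD 150, both equal to 1.5 SD. Then 1.5/√(2/23) = 5.09, and power = Φ(5.09 − 1.96) = 0.999; the noncentral t with 44 df also gives 0.999. The claim reproduces, but it does not bear on ketones.

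**Objectives against analyses (SAP 2.1.3 and 3.5).**

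| PD endpoint | Verb in objective | Change from baseline? | Planned analysis |
|---|---|---|---|
| MMTT hormone AUCs | evaluate | yes | as primary (ANCOVA) |
| Fasting FFA | compare | yes | as primary (ANCOVA) |
| β-hydroxybutyrate | compare | no | descriptive |
| 24-hour urinary glucose | evaluate | no | descriptive |

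Ketones are the only PD endpoint with a comparative objective and no comparison. FFA, which shares the ketosis rationale in Protocol 3.2.3.3, has one.

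**Is there a usable baseline?** Yes, for Day 28. The Day -1 profile is taken on dapagliflozin, before any injected study drug, at the same nominal times and with the same drink 2 hours after dosing. It is not meal-matched to Days 7 and 14. On any one day, however, both arms get the same meal, so a same-day contrast between arms is fair.

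**Which window?** Twelve hours is the longest span sampled alike on all four profile days. The next-morning samples fall on Days 1, 8, 15 and 29. The schedule marks an overnight fast for Day 1 but not for Days 8, 15 or 29, so a 24-hour window would end on samples without a common fasting requirement.

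**Precision with 23 per arm.** Half-width of the 95% CI, in units of the between-subject SD:

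- Unadjusted: t(0.975, 44) × √(2/23)
- ANCOVA: t(0.975, 43) × √(1 − r²) × √(2/23), where r is the Day -1/Day 28 correlation

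The documents give neither r nor a ketone SD, so r is an assumption. The last two columns also assume a log-scale SD of 0.5 or 0.7 and show the factor exp(half-width × SD) by which the ratio is multiplied and divided.

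| Analysis | Half-width (SD) | Factor, SD 0.5 | Factor, SD 0.7 |
|---|---|---|---|
| Unadjusted | 0.594 | 1.35 | 1.52 |
| ANCOVA, r = 0.3 | 0.567 | 1.33 | 1.49 |
| ANCOVA, r = 0.5 | 0.515 | 1.29 | 1.43 |
| ANCOVA, r = 0.7 | 0.425 | 1.24 | 1.35 |

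With 20 evaluable per arm, the ANCOVA half-widths are 0.611, 0.555 and 0.458 SD for the same three correlations.

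**AUC0-inf.** This parameter adds Clast/λz to the observed area, which presumes decay to zero. As an illustration, assume a profile that settles on an endogenous plateau: 0.2 mmol/L plus 0.3·exp(−0.2t). Fitting λz to the 6, 8 and 12 hour points gives 0.0399 per hour. With C(12) = 0.227, the extrapolated part is 0.227/0.0399 = 5.69, against an observed 0-12 h area of 3.76. Extrapolation is then 5.69/(5.69 + 3.76) = 60% of the total. A plateau of 0.3 with the same decaying part gives 70%, and a plateau of 0.2 with a decaying part of 0.1 gives 82%. A flat profile gives λz = 0 and no finite value. SAP 3.8 lists Cmax, tmax, Cτ, AUCτ and accumulation ratio for ketones. It limits the terminal-phase parameters to MEDI0382 and dapagliflozin, and describes neither AUC0-inf nor AUC0-last.

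**The case against.** The endpoint is exploratory, in an exploratory Phase 2a trial, and the SAP removed nothing. Protocol 4.8.3.3 leaves ketones off the list analyzed like the primary, and Protocol 4.8.5.1 plans only parameter estimation. Urinary glucose is descriptive too. Ketoacidosis is also watched by other means: daily capillary ketones, scheduled pH, bicarbonate and lactate, and adverse event reporting. The protocol rates the clinical risk of ketoacidosis as very low. All of this stands and limits the weight of the point. It does not close the gap between objective and analysis, which both documents share. Exploratory status does not explain the gap either, since hormone AUCs and FFA are equally exploratory and are modeled.

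A reader might infer more than the documents support:

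- *The trial cannot estimate a ketone effect.* It can. Arms are randomized and profiled on the same days, and by-arm means and SDs would give an unadjusted difference with an interval.
- *Day -1 is unused.* It may well be summarized, since summaries are given at each time point. It is unused only as a baseline.
- *Placebo ketones will not be reported.* SAP 3.8 does say "the following summary statistics will be calculated for each active treatment group", and the ketone sentence in SAP 3.5.1.2 does not repeat that results are shown by arm. But that section places PD analysis on the ITT population, SAP 3.8 derives parameters for subjects in each treatment group, and the Ketone PK Population in SAP Table 3.2-1 includes placebo recipients. This is ambiguous wording that needs one clarifying sentence.
- *The change of meal spoils the analysis.* No trend across dose levels is planned, so there is no such analysis to spoil. The meal matters only in choosing which day Day -1 is matched to.

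The gain from adjustment is also uncertain: at r = 0.3 the half-width falls by only about 5% (0.594 to 0.567 SD).

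**Conclusion.** The point holds as a gap in prespecification. The objective promises a comparison, and SAP 3.5.1.2 supplies no contrast, no interval and no baseline adjustment, although the data and a meal-matched Day -1 profile are collected. AUC0-inf is a poor parameter for this analyte and has no stated ketone calculation; Cmax and a fixed-window AUC are unaffected.

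With 23 per arm, a prespecified analysis would give a 95% CI half-width of about 0.43 to 0.57 SD for correlations of 0.7 down to 0.3, against 0.594 SD without adjustment. The correlations are assumptions, as are the log-scale SDs behind the ratio factors and the plateau profiles behind the 60% to 82% extrapolation. The finding itself does not depend on them: the plan as written states no between-arm estimate at any precision.

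**What to change.** In SAP 3.5.1.2:

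- Analyze Day 28 log AUC(0-12h) and log Cmax of β-hydroxybutyrate by ANCOVA with treatment and the corresponding log Day -1 value, in the ITT population that the section already names. Report the MEDI0382/placebo ratio with its 95% CI.
- Give the same-day between-arm contrasts for Days 7 and 14 as supportive, noting that their meal differs from that of Day -1. For the same reason, do not carry Day 14 values forward to Day 28.
- State that ketone parameters are summarized for both arms.
- Drop AUC0-inf for ketones, keep Cmax and the fixed-window AUC, and add the AUC(0-12h) calculation to SAP 3.8.

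The cost is a few lines of SAP text and one further model on data already collected. The log scale needs a stated rule for values below the quantitation limit. The result should be labeled exploratory and read through its interval, since SAP 3.1 makes no multiplicity adjustment.

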### 3.6 Safety Analyses

#### 3.6.1 Adverse Events and Serious Adverse Events

Adverse events (AE) will be coded by MedDRA version 20.0 or higher. Analysis of adverse events will include the type, incidence, severity and relationship to study investigational product (MEDI0382 or dapagliflozin) summarized by MedDRA System Organ Class (SOC) and Preferred Term by treatment group as well as for overall treatments. The AEs summaries will include only treatment-emergent AEs; ie, those occurring after initial receipt of investigational product. Subjects will be counted once for specific PT or MedDRA SOC when calculating incidence. If the same AE Preferred Term occurs multiple times within a subject, the highest severity and level of relationship observed will be reported. Non-treatment-emergent AEs/serious adverse events will be presented in the listings.

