1.6 Benefit-risk and Ethical Assessment

The study will be performed in accordance with ethical principles that have their origin in the Declaration of Helsinki and are consistent with International Council for Harmonization (ICH)/Good Clinical Practice (GCP) and applicable regulatory requirements.

MEDI0382 is a GLP-1 and glucagon receptor coagonist that promotes glucose lowering and weight loss and is targeted at subjects with T2DM. MEDI0382 has the potential to deliver improvements in glycemic control and lipid homeostasis, and it is predicted to be a useful therapy for T2DM.

The study design aims to minimize potential risks to subjects participating in this study based on the proposed inclusion/exclusion criteria, safety monitoring, and uptitration dosing schedule. Euglycemic diabetic ketoacidosis (eDKA) and hypovolemia are rare potential risks in subjects taking SGLT2 inhibitors. All subjects will be monitored throughout the study to ensure adequate glycemic control, ketones production, and intravascular volume status. Subjects will be given appropriate training in subcutaneous (SC) injection administration as well as use of any devices. Refer to the current MEDI0382 IB and dapagliflozin IB for further information on the potential benefits of MEDI0382 and dapagliflozin and an assessment of the potential and known risks. Identified risks for this study include nausea and vomiting. Potential risks for this study include hypoglycemia, volume depletion, and diabetes ketoacidosis (DKA).

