3.1.2 Treatment Regimen

Four-week run-in period

Following screening, subjects previously treated with metformin monotherapy only will enter an open-label, run-in period and will receive oral dapagliflozin 10 mg a day for 4 weeks, which will be provided by the sponsor.

Four-week treatment period

Following the run-in period for subjects on metformin monotherapy or the screening period for subjects on metformin and dapagliflozin dual therapy, subjects will be randomized as follows:

- MEDI0382 SC once daily (titrated up from 100 µg for 7 days to 200 µg for 7 days and to 300 µg for 14 days) in the morning for 28 days (N = 23) or
- Placebo SC once daily in the morning for 28 days (N = 23)

The sponsor will provide dapagliflozin to all subjects entering the treatment period.

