3.2.1.2 MEDI0382

To date, the development program for MEDI0382 has studied doses up to 300 µg as part of a multiple ascending dose study (D5670C00002). The 300 µg dose has been specifically studied for a period of 7 days in 2 separate cohorts, each exploring different uptitration schedules to reach this dose. At the 300 µg dose level, the safety and tolerability profile was comparable with previous clinical data with lower doses of MEDI0382 and other GLP-1 mimetics at this stage of development, and there was no increase in systolic or diastolic BP. In fact, a nonsignificant trend towards reduction of systolic BP was observed (~2-5 mmHg reduction across the cohorts after data correction for placebo). Across the 2 cohorts, the LS mean for percent change from baseline to the end-of-treatment period in glucose AUC_{0-4h}

following a MMTT was -36.73% to -41.65% in MEDI0382-treated subjects versus -8.02% to -14.54% in placebo-treated subjects. The LS mean for change from baseline in body weight was -2.07% to -3.40% in MEDI0382-treated subjects versus -0.68% to -0.86% in placebo-treated subjects. Of note, no events of DKA have been observed in the MEDI0382 development program to date.

The current study intends to minimize the likelihood of observing adverse effects by titrating MEDI0382 up to 300 µg (ie, the highest dose previously tested). In addition, this study ensures that all doses that are likely to be included in later stages of MEDI0382 development (ie, 100 µg through 300 µg) are studied in combination with dapagliflozin.

Similar studies conducted with exenatide in combination with dapagliflozin showed no significant impact on the PK of either drug in the combination arm, despite the delay in gastric emptying due to the GLP-1 component of exenatide. Furthermore, given the earlier time to maximum-observed serum drug concentration (t_{max}) of dapagliflozin (~1 hour) compared to MEDI0382 (~4 hours), the potential for additional delay in gastric emptying due to the glucagon component of MEDI0382 is not deemed to be relevant to the absorption phase of dapagliflozin. Therefore, it is expected that MEDI0382 and dapagliflozin will retain their typical PK profile in the presence or absence of the coadministered drug.

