5.4.1 Time Period for Collection of Adverse Events

All AEs and SAEs will be collected from the time of admission to the clinical unit (Day -2) throughout the treatment period and including the follow-up period (28 ±4 days after the last dose of investigational product (inpatient Visit 13).

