### 2.1.2 Secondary Study Objectives

- To compare the safety and tolerability profile of MEDI0382 (titrated up to a dose level of 300 µg subcutaneous [SC]) compared to placebo after 28 days of treatment in subjects treated with dapagliflozin and metformin
- To evaluate the pharmacokinetics (PK) profile of MEDI0382 and dapagliflozin (in subjects treated with dapagliflozin, metformin, and MEDI0382) and dapagliflozin (in subjects treated with dapagliflozin, metformin, and placebo)
- To evaluate 24-hour glucose control as measured by continuous glucose monitoring (CGM) in subjects treated with dapagliflozin and metformin receiving MEDI0382 or placebo for 28 days

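### The planned adverse event tables have no dose or time dimension; a descriptive table by period of onset would show when nausea and vomiting arise

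*SAP*

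**What the plan says.** **Adverse event tables.** In SAP 3.6.1, events are "summarized by MedDRA System Organ Class (SOC) and Preferred Term by treatment group as well as for overall treatments". On counting: "Subjects will be counted once for specific PT or MedDRA SOC when calculating incidence". On the window: "The AEs summaries will include only treatment-emergent AEs; ie, those occurring after initial receipt of investigational product". Protocol 4.8.4.1 has the same scheme, and SAP 3.6.3 summarises deaths and discontinuations due to adverse events by treatment. Protocol 5.4.1 collects events "throughout the treatment period and including the follow-up period (28 ±4 days after the last dose of investigational product".

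**Identified risks.** Protocol 1.6: "Identified risks for this study include nausea and vomiting". The only adverse event of special interest is hepatic (Protocol 5.3.1, SAP 3.6.2), and no separate nausea or vomiting analysis is specified.

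**Dosing.** Protocol 3.1.2 has MEDI0382 "titrated up from 100 µg for 7 days to 200 µg for 7 days and to 300 µg for 14 days". Protocol 3.1.3 escalates placebo on the same steps.

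**Purpose.** Protocol 3.2.1.2 says that "this study ensures that all doses that are likely to be included in later stages of MEDI0382 development", given there as 100 to 300 µg, are studied with dapagliflozin. The safety objective in SAP 2.1.2 opens "To compare the safety and tolerability profile of MEDI0382 (titrated up to a dose level of" and goes on to 300 µg, compared with placebo after 28 days.

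**The concern.** Most other outcomes can be lined up with the dose in force. The CGM endpoints are taken at the end of each dose level (SAP 3.4.2.1), and MEDI0382 PK parameters are estimated at each dose level (Protocol 4.8.5.1). Laboratory values, vital signs with ambulatory blood pressure, and ECG are summarised at each time point (SAP 3.6.4 and 3.6.5). The adverse event tables have neither dimension, yet they are where the identified risks appear.

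Tolerability at 300 µg is also where this trial adds most. The earlier study gave that dose for 7 days (Protocol 1.4 and 3.2.1.2). Here it is given for 14 days, in a combination not studied before. Nausea confined to the first week and nausea that begins at the maintenance dose would be read differently when later studies are planned, but both can produce the same planned table. Events starting after the last dose fall into the same count.

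**Working it through.** The plan gives no figure on this point to reproduce. The check sets out what the planned count can and cannot distinguish.

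**1. Composition of the window, for a completer.** Dosing is 7 + 7 + 14 = 28 days (Protocol 3.1.2), and follow-up is 28 ± 4 days (Protocol 5.4.1).
- Nominal window: 28 + 28 = 56 days. At 300 µg: 14/56 = 25%. After last dose: 28/56 = 50%.
- With 24 days of follow-up: 14/52 = 26.9% and 24/52 = 46.2%.
- With 32 days of follow-up: 14/60 = 23.3% and 32/60 = 53.3%.

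These are shares of calendar time. They are not shares of events and do not measure bias.

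**2. Plausible counts.** Protocol 3.2.3.2 gives maximum cohort rates of 41.7% for nausea and 27.3% for vomiting in the cohorts titrated to 300 µg. These match 5/12 and 3/11. The denominators are inferred, and they sum to the 23 subjects mentioned there. Applied to 23 per arm:
- nausea: 0.417 × 23 = 9.6, about 10 subjects;
- vomiting: 0.273 × 23 = 6.3, about 6 subjects.

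**3. What one total allows.** Assume that 10 of 23 MEDI0382 subjects ever report nausea. Let k be the number with an onset during the 300 µg period; the planned table restricts k only to 0 ≤ k ≤ 10. Exact 95% limits for x of n are the 2.5% quantile of Beta(x, n − x + 1) and the 97.5% quantile of Beta(x + 1, n − x), with a lower limit of 0 when x = 0.

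| Quantity | Estimate | 95% CI |
|---|---|---|
| Planned table, 10/23 | 43.5% | 23.2% to 65.5% |
| At 300 µg if k = 0 | 0% | 0% to 14.8% |
| At 300 µg if k = 5 | 21.7% | 7.5% to 43.7% |
| At 300 µg if k = 10 | 43.5% | 23.2% to 65.5% |

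A table by period of onset would replace the range of 0% to 43.5% with one observed value.

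**4. Denominator.** The as-treated denominator includes anyone who stopped before Day 15. If, as an assumption, 5 of 23 had stopped, 18 would be at risk at 300 µg. The same 5 subjects with nausea would then be 5/18 = 27.8% instead of 5/23 = 21.7%.

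**5. Precision.** Spread evenly over four periods, 10 and 6 subjects give averages of 2.5 and 1.5 per cell. The added table can describe timing but cannot support tests.

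**The case against.** The strongest case against has six parts.

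- **The data are not lost.** A reader might infer that tolerability at 300 µg cannot be learned from this trial. The documents do not support that. Dose steps fall on fixed days (1, 8 and 15), the treatment-emergent definition needs onset timing, and SAP 3.1 plans subject-level listings sorted by date where appropriate. SAP 3.3.3 also tabulates days dosed, which indicates how many subjects stayed on long enough to reach 300 µg. This part stands: the gap is in the planned summaries only. A listing, however, gives no prespecified rates, denominators or placebo column.
- **Counting once per subject is ordinary.** It might be read as the fault. It is not, because the same rule works within each period. What is missing is stratification by onset.
- **The objective is met.** It concerns the titrated regimen against placebo, and a by-arm table answers that. The dose rationale in Protocol 3.2.1.2 sets no adverse event endpoint by dose. This stands, and it is why the by-arm table should stay.
- **The table may exist elsewhere.** SAP section 1 puts table templates in a statistical programming plan that is not available here. The SAP describes itself as detailing the summaries for each objective, so a sentence there is still warranted.
- **Placebo is not a clean control in each period.** Because both arms step up together, one might infer a randomised comparison within every period. That holds for Days 1-7. Later periods contain only subjects still on treatment, and remaining on treatment may depend on tolerability.
- **Dose cannot be separated from time.** Titration is forced, so time on drug and adaptation move with dose. This stands and limits the table to description.

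**Conclusion.** The point holds as a cheap improvement to an exploratory Phase 2a plan. The specified summaries give one count per arm over about 56 days, half of them after the last dose, and cannot place nausea or vomiting at 100, 200 or 300 µg or after dosing. In the illustration, 10/23 is compatible with anything from 0% to 43.5% at 300 µg.

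No planned estimate is shown to be wrong, and the documents do not contradict themselves here. The illustration assumes 23 treated subjects and nausea close to the earlier maximum cohort rate. The conclusion also assumes that adverse event onset dates are recorded, which the treatment-emergent definition implies, and that the programming plan does not already contain such a table, which cannot be checked.

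**What to change.** Keep the by-arm table in SAP 3.6.1 and add one descriptive table, without tests:

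- **Rows:** all treatment-emergent events, serious events, events leading to discontinuation, nausea, vomiting.
- **Periods of onset:** Days 1-7, Days 8-14, Day 15 to last dose, after last dose. For subjects who stop early, the last period starts after their own last dose. State which period takes an event that starts on a step-up day.
- **Columns:** both arms in the same periods.
- **Counting:** each subject once per period, with the number entering that period shown as the denominator.
- **Footnote:** dose is confounded with time on treatment; later on-treatment periods include only subjects who remained on treatment, so between-arm contrasts there are not fully randomised; cell counts are small.

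The cost is a few lines of SAP text and one table built from adverse event and dosing dates. Sample size, data collection and dosing do not change. If the programming plan already has the table, one cross-reference in SAP 3.6.1 is enough.
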